4.7.3.3. ECG

12-lead ECG measures (PR, QRS, QT, and QTc intervals) will be reported based on GSK Core Data Standards. Change from baseline in ECG measures will be summarised by treatment group and visit. Multiple assessments recorded on the same day will be dealt with as per Section [6.2.5](#)

4.8. Immunogenicity Analyses

4.8.1. Occurrence of anti-drug antibodies (ADA) and neutralising antibodies (NAb)

For the immunogenicity assessment, two types of anti-drug antibody (ADA) assays will be performed, a binding anti-drug antibody assay and a neutralizing antibody assay.

For the binding assay, there will be a three-tiered analysis: screening, confirmation and titration. The screening assay produces a result of positive or negative relative to a screening cut point. Positive samples continue with the confirmation assay, which also produces a result of positive or negative relative to a confirmation cut point. For positive confirmation samples, a titre value will also be obtained to quantify the degree of binding in a titration assay and the sample will be tested with the neutralizing assay, which also reports results as positive or negative.

The binding ADA results at each visit will be categorised as negative, transient positive (defined as a single confirmatory positive immunogenic response that does not occur at the final study assessment) or persistent positive (defined as a confirmatory positive immunogenic response for at least 2 consecutive assessments excluding the baseline visit, or a single result at the final study assessment). In addition, the highest post-baseline binding ADA confirmatory result obtained for a participant will be summarised. Participants with both positive and negative results will be identified in the positive category. Summary statistics for the titre result by visit will also be presented.

Neutralizing antibody assay results will be summarised by visit. In addition, the highest post-baseline neutralising antibody assay result during the treatment period of the study will be summarised, with participants with both positive and negative results identified in the positive category.

Furthermore, a summary of on-treatment adverse events (AEs) by highest post-baseline binding ADA confirmatory assay result [positive / negative] will also be generated.

Immunogenicity data will be listed for participants within the Full Analysis Set.

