Potential risk of immunogenicity	
 • Biopharmaceutical products may elicit anti-drug antibody (ADA) and neutralising antibodies (NAb), which have the potential to modulate pharmacokinetics (PK), pharmacodynamics (PD) or produce adverse reactions. However, humanised and fully human antibodies are less immunogenic than mouse or chimeric monoclonal antibodies. • In a placebo-controlled study of severe HES in adolescent and adult participants, the incidence of immunogenicity following mepolizumab administration was low. ADA were seen in 1 (2%) participant at baseline and 1 (2%) participant at Week 32. Both participants were in the mepolizumab treatment group and had low titre values and unremarkable AE profiles. Immunogenicity data reported to date across the mepolizumab development program are summarised in the IB; see Section 5.4, 'Clinical Immunogenicity' and a summary of immunogenicity findings in the 'Other Potentially Clinically Relevant Information for the Investigator' section located in Section 6 titled 'Summary of Data and Guidance for the Investigator'. 	
 • To characterise the potential risk of immunogenicity, blood samples are collected in clinical studies for detection of ADA and NAb.

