1.1. Objectives, Estimands and Endpoints

Objectives	Endpoints
Primary	

 To evaluate the efficacy of mepolizumab SC given every 4 weeks in participants aged 6 to 17 years with HES. 	
 Frequency of HES flares over the 52-week study treatment period.
Secondary	

 To assess the effect of mepolizumab SC given every 4 weeks on the change in oral corticosteroid (OCS) dose in participants aged 6 to 17 years with HES that are taking OCS at baseline. 	
 Change in the mean daily OCS dose (prednisone/prednisolone or equivalent) from Weeks 0 to 4 to Weeks 48 to 52. Reduction of $\geq 50\%$ in mean daily OCS dose (prednisone/prednisolone or equivalent) from Weeks 0 to 4 compared with Weeks 48 to 52. Achieving a mean daily OCS dose (prednisone/prednisolone or equivalent) of ≤ 7.5 mg during Weeks 48 to 52.

 To assess the effect of mepolizumab SC given every 4 weeks on the change in oral corticosteroid (OCS) dose in participants aged 6 to 17 years with HES. 	
 Achieving a mean daily OCS dose (prednisone/prednisolone or equivalent) of ≤ 7.5 mg during Weeks 48 to 52.

 To assess the efficacy of mepolizumab SC given every 4 weeks on fatigue in participants aged 12 to 17 years with HES. 	
 Change from baseline in fatigue severity based on weekly average score of Brief Fatigue Inventory (BFI) item 3 (worst level of fatigue during past 24 hours) for Week 52.

 To evaluate the immunogenicity of mepolizumab SC given every 4 weeks in participants aged 6 to 17 years with HES. 	
 Occurrence of anti-drug antibodies (ADA) and neutralising antibodies (NAb).

 To assess the effect of long-term use of mepolizumab SC on a pharmacodynamics (PD) marker in participants aged 6 to 17 years with HES. 	
 Ratio to baseline in absolute blood eosinophil count at discrete time points during the 52-week study treatment period.

 To assess the pharmacokinetics (PK) of mepolizumab SC in participants aged 6 to 17 years with HES. 	
 Mepolizumab plasma concentration at discrete time points during the 52-week study treatment period.

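### The participant-level ADA and NAb summaries and the AE-by-ADA table do not take account of baseline status, and no treatment-emergent definition is given

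*SAP*

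**What the plan says.** The secondary immunogenicity objective (Protocol Section 3, SAP 1.1) has the occurrence of ADA and NAb as its endpoint. Neither document words it as treatment-emergent. SAP 4.8.1 plans these displays:

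- **By visit.** "The binding ADA results at each visit will be categorised as negative, transient positive" or persistent positive. Titre statistics and NAb results are also given by visit.
- **Transient positive** is "defined as a single confirmatory positive immunogenic response that does not occur at the final study assessment".
- **Persistent positive** is "a confirmatory positive immunogenic response for at least 2 consecutive assessments excluding the baseline visit", or one positive at the last assessment.
- **By participant, ADA.** "the highest post-baseline binding ADA confirmatory result obtained for a participant will be summarised", with the rule that "Participants with both positive and negative results will be identified in the positive category".
- **By participant, NAb.** "the highest post-baseline neutralising antibody assay result during the treatment period of the study will be summarised", with the same rule for mixed results.
- **Adverse events.** On-treatment events are summarised by the participant's highest post-baseline ADA result, positive or negative.
- **Listing.** Immunogenicity data are listed for the full analysis set.

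The Schedule of Activities (Protocol Table 1) places immunogenicity samples at Visit 2 (Week 0), Week 24, Week 52 and follow-up, with further samples after early discontinuation or withdrawal. Protocol 8.6 says samples are taken before dosing.

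**The concern.** The objective concerns the immunogenicity of mepolizumab, that is, antibody the drug induces or boosts. With no placebo arm to show background positivity, the Visit 2 sample is the only control within the study. The participant-level ADA and NAb summaries and the adverse event table do not use it. Antibody that was present before dosing and did not change would appear in the same line as antibody that arose on treatment.

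Pre-existing antibody is plausible on the documents' own evidence. In the earlier placebo-controlled HES study, "ADA were seen in 1 (2%) participant at baseline and 1 (2%) participant at Week 32" (Protocol 2.3.1, Table 2). Protocol 5.2 excludes mepolizumab only in the 4 months before enrolment, so earlier exposure is possible.

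What is at stake is the percentage quoted as the immunogenicity result and the make-up of the ADA-positive column in the adverse event table. That column is likely to hold very few participants.

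**Working it through.** The documents give no expected ADA or NAb rate, so there is no planned figure to reproduce. The check has two parts.

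**1. Applying the definitions to possible result patterns**

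The order is Week 0, Week 24, Week 52, follow-up. The titre is unchanged unless stated.

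| Pattern | Highest post-baseline ADA | Transient / persistent under SAP 4.8.1 | Treatment-emergent? |
|---|---|---|---|
| A: − + + + | Positive | Persistent | Yes |
| B: + + + + | Positive | Persistent | No |
| C: + + + +, titre rise | Positive | Persistent | Yes, if above a pre-set threshold |
| D: + + − − | Positive | Transient if the baseline positive is not counted. Neither category if it is: there are then two positives, so not a single one, but only one after baseline, so not two consecutive | No |
| E: + − − − | Negative | Transient if the baseline positive is counted, otherwise negative | No |

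Patterns A, B and C look the same in the participant-level summary and in the adverse event table. The baseline exclusion in the persistent definition stops the Week 0 result counting towards the two consecutive positives. It does not remove a baseline-positive participant, so B is still persistent. Patterns D and E depend on whether the transient definition counts Week 0, which the SAP does not say.

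**2. Size**

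Inputs: N = 15 (Protocol 9.2, SAP Section 5). Baseline positivity p = 2%, borrowed from Protocol Table 2 and so from another population; the range 1% to 10% is an assumption.

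Chance of at least one baseline positive among 15 = 1 − (1 − p)^15:

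| p | Chance |
|---|---|
| 1% | 14.0% |
| 2% | 26.1% |
| 5% | 53.7% |
| 10% | 79.4% |

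Effect of one participant with pattern B (exact Clopper-Pearson 95% intervals):

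- With no other positives, the plan reports 1/15 = 6.7% (0.2% to 31.9%). The treatment-emergent figure is 0/15 = 0% (0% to 21.8%), or 0/14 = 0% (0% to 23.2%) among those negative at baseline.
- With one new positive as well, the plan reports 2/15 = 13.3%. The treatment-emergent figure is 1/15 = 6.7%, or 1/14 = 7.1%.

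In the first case the pre-existing positive is the whole ADA-positive column of the adverse event table; in the second it is half of it. If the summaries are also split by age, one such participant among the planned minimum of 4 adolescents is 1/4 = 25%.

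The expected inflation is smaller. It is p times the probability of staying positive, so at p = 2% it is at most 2 percentage points.

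**The case against.** The strongest case against is that the plan reports the endpoint as the protocol words it. The endpoint is occurrence, no document requires a treatment-emergent definition, nothing is tested, and the exact intervals above overlap heavily. An adverse event table with perhaps 0 to 2 positive participants supports little comparison under any definition. All of this stands, and it limits the weight of the point. It does not change the fact that pre-existing and new antibody are merged.

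Three stronger readings are tempting, and the documents do not support them:

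- *The SAP ignores the baseline sample.* It does not. The sample is taken at Visit 2, the ADA, titre and NAb results are summarised by visit, and the persistent definition leaves baseline out of its count.
- *The treatment-emergent figure could not be recovered.* The by-visit tables do not link a participant's results, but SAP 4.8.1 commits to a listing. With about 15 participants and about four scheduled samples each, the pairs can be read from it. SAP 4.1 does not say which listings go into the study report, so its place there is not certain.
- *Any baseline positive inflates the proportion.* Only one who is positive again after baseline does. Pattern E never enters the post-baseline summaries or the adverse event table; only its transient label is in doubt.

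The earlier study also needs care. Protocol Table 2 refers to its two positives as both participants, which reads as two different people. It shows that baseline positivity occurs, not that it persists.

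**Conclusion.** The point holds as a reporting gap in a descriptive secondary endpoint. Because the participant-level ADA and NAb summaries and the AE-by-ADA table do not depend on baseline status, a participant positive before dosing who stays positive without a titre rise is reported as a post-baseline positive. Each such participant adds 6.7 percentage points at N = 15. Whether there will be one is uncertain: the 26.1% chance rests on carrying the 2% over from another study, and it concerns any baseline positive, not one that persists. The uneven wording of the transient and persistent categories is a separate, smaller defect that leaves patterns D and E open to different programming. The sample size and the primary flare analysis are not affected.

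**What to change.** In SAP 4.8.1, before database lock:

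1. Cross-tabulate baseline by highest post-baseline status, for ADA and for NAb.
2. Define treatment-emergent ADA as negative at baseline and positive afterwards, or positive at baseline with a titre rise above a stated threshold. Report it separately from pre-existing ADA. The documents give no assay characteristics, so the sponsor must justify and fix the threshold.
3. For NAb, which has only positive or negative results, report baseline negative to positive separately from pre-existing. Only confirmed ADA positives go to the NAb assay, so state that a baseline sample negative for ADA counts as NAb negative.
4. Use treatment-emergent status in the AE-by-ADA table.
5. Add to the transient definition the baseline exclusion that the persistent definition already has. Pattern D then becomes transient and pattern E is no longer a positive category.

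The cost is SAP wording, one small table per assay, slight extra programming and the choice of a titre threshold. The samples and titres are already planned, so participants carry no added burden.

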- Assessments will be collected when possible depending on the clinical status during worsening of symptoms between scheduled clinic visits to evaluate for a HES flare. When attending the clinic visit at the time of a suspected HES flare is not possible, the investigator should make every effort to evaluate the participant via telephone and complete the HES Core assessments v2.
- Subjects who prematurely discontinue study treatment will continue to attend 4-weekly scheduled Discontinuation Visits completing assessments as indicated. Participants who discontinue study treatment are not required to perform a Follow-up visit, unless they have not completed 12 weeks after last dose immunogenicity assessment within the 52 week study period.
- Informed consent must be obtained prior to starting Visit 1 procedures.
- Parasitic screening is only required in countries with high-risk or for participants who have visited high-risk countries in the past 6 months. Sites should use local laboratories.

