9. CCI [REDACTED]
[REDACTED]
10. When a CV flare is suspected during the study period based on investigator's judgement.
11. Only SAEs that are considered related to study procedures are to be collected from the time of signing informed consent.
12. Vital sign measurements will include temperature, systolic and diastolic blood pressure, and heart rate.
13. During the treatment period, all laboratory samples should be obtained pre-dose.
14. Eosinophil count samples for the screening visit only may be analysed by local labs if required. If a local sample is required, it is important that a sample for central analysis is obtained at the same time. Local lab eosinophil count results performed at the screening visit will be entered to the eCRF. If local lab samples are taken, a second sample will also be sent for central testing. The higher of the eosinophil cell count values is to be used to fulfil the entry criteria for enrolment.
15. Do not perform for each discontinuation visit, follow test frequency of Treatment Period schedule visit 2-15.
16. Negative urine pregnancy test result must be confirmed prior to dosing in female participants of reproductive potential. If a urine test cannot be confirmed as negative (e.g., an ambiguous result), a serum pregnancy test is required. In such cases, the participant must be excluded from participation if the serum pregnancy result is positive.
17. Pregnancy testing is only required until the end of systemic exposure, 12 weeks after the last dose.
18. Urine tests are done locally using dipstick. If found abnormal, the urine sample will be sent to the central laboratory for further testing.
19. If test was performed within 3 months prior to Visit 2, testing at Screening is not required. Test required are hepatitis B surface antigen and hepatitis C antibody. Participants with positive hepatitis C antibody due to prior resolved disease can be enrolled only if a confirmatory negative hepatitis C RNA test is obtained.
20. If no documented results are available.
21. For participants who discontinue treatment immunogenicity is to be performed 4 and 12 weeks after the last dose only.
22. For participants who discontinue treatment PK is to be performed 4 weeks after last dose only.
23. The date and time of the administration of study treatment will be recorded in the eCRF.

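### SAP 4.8.1 limits the participant-level NAb result to the treatment period but not the matching binding ADA result, so a NAb positive seen only at follow-up is not counted (minor)

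*SAP*

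**What the plan says.** Occurrence of ADA and NAb is a single secondary endpoint (Protocol Section 3, Table 3; SAP 1.1) and carries no time limit. The blood eosinophil and plasma concentration endpoints listed beside it are both tied to the 52-week treatment period.

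SAP 4.8.1 gives two participant-level summaries:

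- Binding ADA: "the highest post-baseline binding ADA confirmatory result obtained for a participant will be summarised". The persistent-positive category also accepts a lone positive at the end of the study: "or a single result at the final study assessment".
- NAb: "the highest post-baseline neutralising antibody assay result during the treatment period of the study will be summarised".

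The same section adds that "Neutralizing antibody assay results will be summarised by visit", with no period limit, and that immunogenicity data will be listed for the Full Analysis Set. Once a sample is confirmed ADA positive, "the sample will be tested with the neutralizing assay, which also reports results as positive or negative".

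On timing, Protocol 1.1 and 4.1 put the last dose at Week 48, the final treatment-period visit at Week 52 and follow-up 12 weeks after the last dose. Table 1 of Protocol 1.3 schedules immunogenicity at Weeks 0, 24 and 52, at the discontinuation and withdrawal visits, and at Visit 16. Footnote 21 says: "For participants who discontinue treatment immunogenicity is to be performed 4 and 12 weeks after the last dose only". Footnote 3 excuses discontinuers from follow-up "unless they have not completed 12 weeks after last dose immunogenicity assessment within the 52 week study period". EAP entrants have no follow-up visit (Protocol 4.1, 6.6).

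**The concern.** The two halves of one endpoint are summarised over different sets of samples. The protocol goes to some trouble to obtain the 12-week sample, to the point of recalling discontinuers for it. The ADA rules use it and the participant-level NAb rule does not. The section on changes to protocol-defined analyses (SAP 4.11, Table 1) neither lists nor explains the difference.

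At stake is the count of participants who were ever NAb positive. A by-visit table does not supply that count directly, so the highest-result row is the one a reader would cite. In a trial of about 15 participants, one person decides whether that row reads none or one.

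**Working it through.** The plan states no figure that depends on this rule, so there is none to reproduce. The check is calendar arithmetic on the sampling schedule, followed by the size of one reclassification.

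**1. Completers who attend Visit 16.** The last dose is at Week 48, so follow-up is at 48 + 12 = Week 60. The post-baseline samples are at Weeks 24, 52 and 60.

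| Participant-level summary | Week 24 | Week 52 | Week 60 | Samples used |
|---|---|---|---|---|
| Binding ADA | yes | yes | yes | 3 of 3 |
| NAb, as written | yes | yes | no | 2 of 3 |
| NAb, after the fix | yes | yes | yes | 3 of 3 |

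These are samples eligible for the summary. Only those confirmed ADA positive yield a NAb result.

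**2. Completers who enter the EAP.** They have no Visit 16 sample, so nothing changes.

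**3. Discontinuers, taking the treatment period as the 52 weeks.** The 12-week sample falls at last-dose week + 12.

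- Last dose at Weeks 0 to 40: the sample falls at Weeks 12 to 52 and counts. A last dose at Week 40 sits on the boundary (40 + 12 = 52), where the ±7-day windows can move it to either side.
- Last dose at Week 44: the sample falls at Week 56 and does not count. In days from first dose this is 44 × 7 + 84 = 392, or 385 to 399 with ±7 days. The Week 52 visit falls at 364 ± 7, that is 357 to 371, so the two do not overlap.

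**4. Another reading of the period.** SAP 6.2.2 defines phases for flares, other efficacy assessments, adverse events and concomitant medication, but none for immunogenicity. If the adverse-event rule (last dose + 28 days) were borrowed, every 12-week sample would be excluded, since 12 × 7 = 84 > 28. A Week 52 sample taken more than 28 days after the last dose would be excluded too.

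**5. The inconsistent case.** Take a participant outside the EAP who is ADA negative at Weeks 24 and 52, and confirmed ADA positive and NAb positive at Visit 16. For such a participant Protocol 4.4 makes Visit 16 the end of study, so this is the final assessment. Under SAP 4.8.1 the participant is ADA positive, is persistent, and cannot be NAb positive in the highest-result summary.

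**6. Size.** One participant in 15 is 1/15 = 6.7 percentage points.

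**7. How often.** Protocol Table 2 reports ADA in the earlier placebo-controlled HES study in 1 (2%) participant at baseline and 1 (2%) at Week 32. Assume, for illustration only, 2% at Visit 16 with all 15 participants attending. The expected number of ADA positives there is 15 × 0.02 = 0.3, and the chance of at least one is 1 − 0.98^15 = 0.26. The inconsistent case also needs a positive NAb result at that visit and none earlier, and EAP entry reduces attendance. On this assumption its chance is below 26%, by an amount the documents do not allow one to compute.

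**The case against.** The strongest reply is that nothing is hidden. A Week 60 NAb result is in the by-visit table and in the listing, and with about 15 participants a reader can find it. That stands. A reader might infer from the quoted sentence that the 12-week sample is left out of the NAb secondary endpoint. The documents do not support this: the endpoint has no time limit, and only one of the two NAb summaries omits the sample.

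A reader might also infer that the omission matters because drug still in the blood at Week 52 masks antibodies. Footnote 17 of Table 1 in Protocol 1.3 does treat 12 weeks after the last dose as the end of systemic exposure, which supports less drug at that point. But the documents give no drug-tolerance limit for the assays, and Protocol 8.6 says only that they are validated. Missed detection at Week 52 cannot be shown from that.

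Nor is understatement certain. It needs a participant outside the EAP, or a late discontinuer, who is confirmed ADA positive and NAb positive at follow-up with no earlier NAb positive.

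Finally, the limit may be deliberate, to describe neutralisation while participants are being dosed. If so, the SAP does not say it, and it does not explain why binding ADA is handled otherwise.

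These replies reduce the weight of the point. They do not remove the mismatch between two adjacent rules for one endpoint.

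**Conclusion.** The point holds as a minor reporting inconsistency. The participant-level NAb summary can miss a positive that the binding ADA summary would reflect, for completers who attend Visit 16 and for discontinuers whose 12-week sample falls after Week 52. Participant-level NAb occurrence could then be understated by 6.7 percentage points per affected participant among 15. This rests on reading the treatment period as ending at Week 52, as Protocol 1.1 and 4.1 do; under a rule of last dose + 28 days more samples would be excluded. The event is likely to be rare. The analysis is descriptive, and no hypothesis test, sample size or efficacy estimate is affected.

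**What to change.** In SAP 4.8.1, replace the time restriction on the highest NAb result with: *at any post-baseline assessment, including the follow-up visit and the 12-weeks-post-last-dose sample*. NAb and binding ADA then use the same samples. Keep the by-visit NAb table. If the sponsor also wants a treatment-period NAb count, show it as an additional row and define that period for immunogenicity in SAP 6.2.2.

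The cost is one phrase in the SAP. The samples are already scheduled, and confirmed ADA-positive samples already go to the neutralising assay.
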